1. PURPOSE OF STUDY

Neuropsychiatric symptoms (NPS) are a distinctive set of behavioral disturbances that are prevalent in mild cognitive impairment (MCI) and Alzheimer's disease (AD), worsening of which, particularly, can accelerate patients' cognitive and functional decline and cause significant distress to caregivers.^{1,2} NPS often co-exist, rendering the need to understand the shared biological mechanisms underlying multiple NPS, which is crucial for the development of effective interventions to address them simultaneously. Notably, we recently discovered a neural circuit shared by MCI and AD patients with multiple NPS; the circuit is composed of 10 frontal-temporal-striatal regions³ and is highly related to both study partner-rated Neuropsychiatric Inventory Questionnaire (NPI-Q) and AD pathology (indexed by cerebrospinal fluid A β /ptau ratio).³ The **goal of this proof-of-concept mechanistic intervention study** is to confirm the causal relationship between this neural circuit and various NPS, by modifying a key region within the neural circuit [i.e. left precentral gyrus (LPG), critical for regulating visual attention⁴] with anodal transcranial direct current stimulation (tDCS).

Why focus on the LPG via tDCS to understand the contribution of this shared neural circuit to NPS? Our previous work on NPS-shared neural circuit shows that while different NPS are associated with the same 10 frontal-temporal-striatal regions, the strength of functional connectivity (FC), as well as its directionality, varies for different NPS. For example, the strength of most FCs in MCI/AD patients with a depressive symptom is lower than that in patients without this symptom, while the strength of most FCs are higher in patients with an anxiety symptom. Across NPS, however, LPG is the only region that has lower FCs with frontal and striatal regions within the circuit whenever a NPS is present.³ LPG, parallel to C3 in the 10/20 EEG system,⁵ is one of the most frequently examined and effective tDCS targets modifying affective, psychiatric, and psychosomatic symptoms, in addition to motor function.⁶⁻⁸ Administering anodal tDCS also enhances the strength of FCs linking LPG to frontal and limbic regions that are part of the NPS-shared neural circuit.⁹⁻¹² Notably, our feasibility study demonstrated our readiness and safety of administering anodal tDCS to C3 in older adults. Synthesizing these separate lines of evidence, we **hypothesize** that administering anodal tDCS to C3 in patients with NPS will result in enhanced activation of LPG and reorganization of NPS-shared neural circuit, both of which will improve NPS.

Aim 1. Determine the effect of tDCS on NPS-shared neural circuit. **H:** After intervention, the active group, relative to the sham group, will have a greater increase in LPG activity, indexed by greater activation in LPG in response to a visual attention task (H1a) and greater increase in resting FC strength between LPG and other regions within the NPS-shared neural circuit (H1b).

Aim 2. Determine the relationship between NPS-shared neural circuit and study partner-report NPS. **H:** After intervention, the active group, relative to the sham group, will have greater improvement in study partner-rated NPS in terms of lower severity and fewer co-existing symptoms (H2a). Changes in LPG task-induced activity combined with an LPG-seeded NPS-shared neural circuit will contribute to the

improvement in study partner-rated NPS across groups (H2b).

Exploratory aim. Examine the relationship between NPS and the coherence between structural and functional aspects of the NPS-shared neural circuit. Cumulative literature suggests that white matter (WM) tracts play a critical role in supporting and shaping brain function.¹³ It is often assumed that FC is dependent on underlying anatomical connections,¹³⁻¹⁵ with decreases in WM integrity in dementia related to reduced functional efficiency.¹⁶ The magnitude of correlation between the structural and functional aspects of NPS-shared neural circuit may implicate the severity of NPS. Here, we will collect diffusion tensor imaging (DTI) at baseline, as part of MRI data acquisition, and examine whether the effects of tDCS on NPS-shared neural circuit and study partner-rated NPS depend on WM integrity. Exploring this question will provide broaden our mechanistic understanding of NPS.

We propose that probing the LPG via tDCS provides a way to experimentally test the causal relationship between our previously discovered NPS-shared neural circuit and study partner-rated NPS. The proposed research is highly innovative, while scientifically grounded, for targeting one brain region that may affect multiple NPS. Validating the hypotheses has the potential to support a future R01 study that directly conducts a Stage 2 trial addressing NPS in MCI or AD, thus ultimately improving patients' quality of life and reducing the caregiver burden.

Exploratory aim 2: Examine blood biomarkers at baseline for predicting cognitive and brain MRI biomarker responses to intervention. Blood neuropathological (amyloid beta [A β] 42, total tau [t-tau], and neurofilament light [NfL]) and neurotrophic biomarkers (brain-derived neurotrophic factor [BDNF], insulin growth factor-1 [IGF-1], and short-chain acylcarnitines [SCACs]) relate to cerebral amyloidosis, neurodegeneration¹⁷⁻¹⁹ and neurogenesis.^{20,21} Blood A β 42 may indicate cerebral amyloidosis,¹⁹ and blood t-tau, and NfL levels have been shown to reflect neurodegeneration across populations (older adults with AD, MCI, or normal cognition).^{17,18} Their blood levels also correlate with their cerebrospinal fluid (CSF) levels, as well as several neuroimaging biomarkers (amyloid plaques, AD-related brain atrophy, and brain hypometabolism).¹⁷⁻¹⁹ Decreased blood A β 42 and increased t-tau and NfL levels were also found in individuals with MCI or AD and were associated with cognitive decline and incident AD over time.¹⁷⁻¹⁹ Preliminary data from colleagues at the University of Minnesota demonstrated that increased baseline plasma t-tau levels correlated with greater cognitive decline in older adults with MCI over time.²² Moreover, plasma phosphorylated tau (p-tau) is a promising biomarker of neuronal injury. A recent study showed that plasma p-tau levels were better biomarkers for both acute and chronic traumatic brain injury than plasma t-tau levels alone - further providing evidence in support of blood biomarkers as surrogate endpoints for treatment responses in neurological conditions such as aMCI and AD.²³

Blood neurotrophic factors have been shown to cross the blood-brain barrier to increase hippocampal volume and memory.^{20,25-32} Higher plasma BDNF levels were linked to better memory, larger hippocampal volume, and reduced risk for AD.^{25,28,29} Whereas higher plasma IGF-1 levels were cross-sectionally associated with better cognition³³ and lower odds of AD,³⁴ longitudinal data have been inconsistent. However, a recent study showed that higher plasma levels of IGF binding protein-3 (IGFBP-3), which are essential for IGF-1 physiological action,³⁵ were associated with decreased risk for dementia.³⁰

2. BACKGROUND AND RATIONALE

Co-existing NPS in MCI, especially those worsening over time, are associated with more rapid cognitive and functional decline and a greater risk of AD.¹ The majority of the existing literature has focused on the neural mechanism and management of individual NPS in MCI/AD.^{36,37} Optimal NPS management,

meaning effective management of multiple NPS simultaneously, is a major challenge in MCI/AD care.²

Feasibility of administrating tDCS in older adults: Previously, 14 cognitively normal older adults (65-85 years) were randomly assigned to active vs. sham tDCS group. TDCS was applied for 20 minutes (as described in the protocol below) while subjects performed, in random order, two computer-based visual attention tasks that also recruit working memory (1-back) and inhibition (color test in Stroop). Participants were asked to make responses as accurately and quickly as possible (10 minutes per task, **Figure 1A**). Active tDCS was anodal stimulation of C3 with cathode on Fp2 (**Figure 1B**). There were no adverse effects. The two groups were similar in baseline global cognition, age, education, and sex. The 20-minute tasks were segmented into four 5-minute blocks with intra-individual variability in reaction time (IIVRT) computed within each block, ensuring the comparability of cognitive performance between the two types of tasks. IIVRT was calculated using standard deviation divided by averaged reaction time of all the trials with correct responses. The active condition induced significantly better cognitive performance (indexed by lower IIVRT) for the last three blocks, compared to the sham condition (**Figure 1C**).

[figure not shown]

Figure 1. tDCS pilot study. **A.** Visual attention tasks (upper: 1-back; lower: Color test in Stroop); **B.** location of the tDCS electrodes; **C.** cognitive performance across four 5-minute blocks between sham and active groups. * p < .05.

[figure not shown]
We propose to examine the influence of LPG, a region within the NPS-shared neural circuit and a region known to regulate visual attention, on the NPS-shared neural circuit and study partner-rated NPS. In the proposed study, we capitalize on a non-invasive brain stimulation process to manipulate the activation and FC strength seeded in LPG. This design will provide an understanding beyond the correlational relationship between the neural circuit and NPS in patients with MCI. TDCS non-invasively induces a low direct current in the cortical region of interest (ROI), with a potential neural mechanism of inducing synaptic changes that affect neural network activity, reflected in changes in both activation and strength of FC, as well as changes in visual attention-dominant tasks.³⁸ LPG is one of the primary tDCS targets for obtaining effects on psychosomatic and affective symptoms⁶⁻⁸; furthermore, tDCS can easily target (i.e., on the cortical surface) and modulate (i.e., produces large effects) the region. Applying an average of 20 minutes of continuous tDCS can yield acute effects for up to 90 minutes, while 2-4 weeks of sessions can yield effects for up to 6 months.³⁹⁻⁴² Most importantly, tDCS is safe and non-invasive, thus, these characteristics together make tDCS an ideal manipulation technique to modify LPG.

Scientific premise and hypothesis: This proposal aims to determine the causal relationship between our recently discovered NPS-shared neural circuit and study partner-rated NPS by stimulating a region within this circuit (LPG). We integrate the evidence from existing literature and our preliminary work that are potentially relevant to what is proposed here: (1) a worsening pattern of NPS in MCI is most

disturbing for cognitive and functional decline¹; (2) a neural circuit (i.e., NPS-shared neural circuit) supports multiple NPS and links to study partner-rated NPS and AD pathophysiology³; (3) the strength of FCs within the NPS-shared neural circuit varies across individual NPS, with LPG exhibiting greater FC strengths with frontal and striatal regions within the circuit but weaker FC strengths with other regions, the latter of which is linked to higher chances of presenting NPS³; (4) LPG is a hub region that regulates visual attention and processing speed^{4,43,44}; (5) anodal tDCS targeting LPG enhances brain synchronization and whole-brain resting-state functional connectivity between LPG and its neighboring regions (particularly frontoparietal regions) or between LPG and caudate⁹⁻¹²; (6) anodal tDCS targeting LPG also modifies affective, psychiatric, and psychosomatic symptoms (e.g., humor, appreciation, anxiety, pain)⁶⁻⁸.

We hypothesize that anodal tDCS stimulating LPG can affect LPG activation (indexed by enhanced neural efficiency during the visual attention task) and its connectivity with other regions within the NPS-shared neural circuit, which, in turn, will reorganize the NPS-shared neural circuit and improve study partner-rated NPS (**Figure 2**). Validating these hypotheses will extend separate bodies of literature on the symptomatic understanding of multiple NPS, neural mechanisms underlying NPS, and the impact of tDCS on neural and behavioral effects, as well as facilitate an explicit elaboration of a shared neural mechanism underlying multiple NPS in MCI. This elaboration has strong potential to inform treatment development for managing multiple NPS simultaneously by addressing the shared neural circuit as the primary therapeutic target. This proposal's significance is further underscored by the implications of our model for potentially preventing AD pathology: our pilot work suggests the NPS-shared neural circuit predicts the trajectory of AD pathology progression, indexed by a change in cerebrospinal fluid A β /ptau ratio. If the neural circuit is modifiable via tDCS applied to the key region within the circuit, this approach may be applicable to

delaying AD pathology from developing and benefit other clinical domains, such as cognitive

deficits and impaired functional **Figure 2. Conceptual framework**

independence, thereby potentially slowing overall AD progression.

3. ADMINISTRATIVE ORGANIZATION

Study-related appointments will be conducted on-site at University of Rochester Medical Center locations. Subjects will be given the option to do the tDCS interventions at the subject's home or at our lab. During home visits, study team members will assess the environment (ex. dog barking, TV on, etc.) and adjust accordingly depending on the specific situation. Regardless of intervention location, a trained study team member will be administering all tDCS interventions. All in-person assessments for this research study will be conducted in [name] Lab (located at the Annex Building). All MRI appointments will be conducted at the Rochester Center for Brain Imaging/Center for Advanced Brain Imaging and Neurophysiology (RCBI/CABIN). Baseline blood collection will be conducted at URMC's Clinical Research Center (CRC).

4. STUDY DESIGN

This is a Stage 0 study for mechanistic understanding. We will recruit older adults with study partner-rated NPS that has worsened in the past 2 years. Our previous study shows that this will capture

the most detrimental type of NPS.¹ We will focus on the MCI group, since understanding and modifying NPS among this group may assist in slowing the progression of dementia. See Table 1 for the overview of assessment and intervention timeline.

- Double-blind randomized controlled trial of 40 participants and their study partner subjects; all eligible and interested intervention subjects will be enrolled and undergo a baseline assessment, MRI scan, and blood draw; PI, staff conducting follow-up assessments and intervention subjects and their study partner subjects will be blinded. Interventionists and data managers will know randomization.
- After baseline, all intervention subjects will be randomly assigned to one of two groups - active anodal or sham C3 tDCS. A MATLAB block-based randomization code will be used to randomly assign study ID to group. Each study ID-group pairing will be printed and placed inside a sealed envelope labeled with only the study ID to ensure blinding. After an intervention subject and their partner subject finish baseline assessments, the interventionist or data manager will open the randomization envelope to assign the respective study ID.
- All intervention subjects will undergo a total of fourteen (14) 20-minute tDCS sessions over the course of four weeks: ideally, five times a week for two weeks, followed by twice a week for an additional two weeks. However, we will extend the intervention for additional two weeks for make-up sessions.
- Assessments will occur at baseline, within 2-week after finishing intervention (post-intervention assessment), and 4 to 6 weeks after post-intervention assessment (follow-up assessment).
- Unblinding will occur upon the completion of the follow-up assessment. We will not provide those in the sham group with the active tDCS procedure.

Primary endpoints:

- Resting-state and visual attention task-related fMRI;⁴⁵

fMRI data will be collected using a gradient echo-planar imaging sequence. Participants will undergo a 5-minute resting-state scan at first, being instructed to relax with their eyes open, followed by a 5-minute event-design ‘target among distractors’ visual search task. For the task, participants fixate on a black screen for a constant inter-stimulus interval of 1000ms, follow by 5500ms presentation of the search pattern. Participants’ task is to search for target symbol “申” (which was present for 50% of trials), shown among 6 distractors (e.g., “由”, “甲”, etc.). Participants are instructed to press one of two response buttons to indicate whether the target was present or absent.

Secondary endpoints:

- Study partner-rated NPS (frequency and severity scores from NPI and NPI-Q⁴⁶).

Other measures:

- Cognitive functions will be measured using tests from three different versions of the computer-based battery Executive Abilities: Measures and Instruments for Neurobehavioral Evaluation and Research (EXAMINER);
- Paper-based measures of cognitive functioning will be measured using two versions of the Rey Auditory Verbal Learning Test (RAVLT, Lists A&B and C&D) and the Brief Visuospatial Memory

Test-Revised (BVMT-R, Forms 1-3);

- Functioning in daily life will be measured with the self-report version of the Activities of Daily Living-Prevention Instrument (ADL-PI-self).
- Fatigue across 5 domains (general, physical, mental, and reduced motivation & reduced activity) will be measured using the Multidimensional Fatigue Inventory (MFI);
- Sleep habits and quality of sleep will be measured using the total score from the Pittsburgh Sleep Quality Index (PSQI);
- Depression will be measured using both the 15- and 30-item versions of the Geriatric Depression Scale (GDS);
- Risk of suicide (current & past) and current suicidal ideation will be measured using Columbia Suicide Severity Rating Scale (C-SSRS);
- Anxiety will be measured using both the state and trait anxiety scales from the State-Trait Anxiety Inventory (STA);
- Perception of stress will be measured using Perceived Stress Scale (PSS);
- Apathy will be measured using the 18-item self-report and informant-rated Apathy Evaluation Scales (AES);
- Quality of life (QoL) across multiple life domains (including physical health, mood, relationships, activities, ability to perform tasks) will be measured using the 13-item self-report and informant-rated Quality of Life in Alzheimer's Disease scales (QOLAD);
- Cognitive reserve will be measured using Cognitive Reserve Assessment Scale in Health (CRASH);
- Decision making and risk-taking behavior will be measured with the 30-item Domain-Specific Risk-Taking scale (DOSPERT)
- Blood biomarkers collected at baseline will be analyzed and compared to changes of cognitive and MRI brain scan cortical thickness outcomes. Diet history will also be measured by asking three questions assessing the intervention subject's consumption of fish oil prior to the blood draw.
- Medication changes will be assessed by asking the intervention subject for an updated list of their prescribed medications. Of note, although we will ensure the stability of the medication (e.g., anti-depressants, antipsychotics, and/or anxiolytics, memory medication) as part of the eligibility criteria (see section 5.a), we cannot ensure the changes of medications throughout the study procedure, which may interfere with the understanding of the proposed mechanism between brain regions and NPS, therefore, we will consider them confounding factors in later analyses.

Alternate forms of cognitive measures (EXAMINER, RAVLT, BVMTR) will be used across time points (see **Table 1** for details) to avoid practice-effects.

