5. INCLUSION AND EXCLUSION CRITERIA

a) Inclusion Criteria:

1. Forty intervention subjects with MCI and comorbid NPS, which have worsened in the past 2 years (as rated by their study-partner subject's responses to the NPI-Q):
 - (1) In the past month, presence of ≥ 2 symptoms; and
 - (2) Compared to two years ago, having ≥ 1 pre-existing symptom whose severity rating has worsened, or having ≥ 1 new symptom;
2. Consensus diagnosis of “mild cognitive impairment due to Alzheimer’s disease” based on 2011 NIA-AA diagnostic criteria by the investigators based on screening information:
 - i. Memory deficits at screening: 1 standard deviation (SD) below age- and/or education- corrected population norms for the Rey Auditory Verbal Learning Test (RAVLT, Lists C&D);
 - ii. Global memory deficits at screening: Montreal Cognitive Assessment (MoCA, Version 2) total score within the range $18 \leq x \leq 26$, after educational adjustment;
 - iii. Preserved activity of daily living: ADL-PI-self total score ≤ 30 ;
 - iv. Absence of dementia.
3. Stable (same dosage, frequency, type) on memory medications for ≥ 3 months before screening;
4. Stable (same dosage, frequency, type) on any anti-depressants, antipsychotics, and/or anxiolytics for ≥ 7 days;
5. Community-dwelling: Intervention subjects live in homes or independent- and assisted-living facilities (i.e. – not nursing home residents, due to the large cognitive variability in nursing home residents);
6. Aged 60-89 years at screening;
7. English-speaking;
8. Adequate visual and hearing acuity for testing;
9. Verified tDCS and MRI safety: Intervention subject should not have any contraindications to either and pass safety screening questions for both (see exclusion section for more information);
10. Capacity to consent, based on responses and ratings to the UCSD Brief Assessment of Capacity to Consent (UBACC) form for this study;

11. Availability of a study partner subject who spends at least several hours per week with the intervention subject, supervises his/her care, and who is willing to accompany the intervention subject to some study visits and participate in the study;
12. Informed consent for study participation obtained by both the intervention subject and his/her study partner subject;
13. Agree to donate 20mL of blood at baseline, after fasting for at least 8 hours (only water and prescribed medicines).

Study partner subject inclusion criteria:

1. Age 18 years or older;
2. English speaking;

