Assessments: Fully eligible participants and their study partner subjects will be notified of their eligibility for the study. Baseline assessments need to be scheduled within one month of in-person cognitive screening. Participants will then be asked to complete baseline measures (assessment, MRI scan, and blood draw), after which they will be randomized to either the active or sham tDCS intervention condition. The blood draw may occur within 2 weeks (before or after) the baseline assessment and MRI scan. The beginning of the intervention phase will start within two weeks after the baseline assessment and blood draw. Follow-up cognitive assessments and MRI scans for each participant will occur within 2 weeks after completion of intervention (i.e., post-intervention assessment) and then 4 weeks after post-intervention assessment (i.e., follow-up assessment). We will allow 2 weeks to make up the follow-up assessment. At the same time points, study partner subjects will be administered the NPI, AES, and QOLAD. Follow-up assessments for study partners can also be conducted over the phone, at the partners discretion.

A detailed overview of data collection measures for screening and assessments can be found below in **Table 1**. To reduce the burden on participants, study partner subjects, and staff, as well as to avoid practice effects of cognitive measures, for individuals who are eligible for the study, their screening data will be used as baseline data; for those who are not eligible for the study, their screening data will only be used for summarizing the reasons for ineligibility.

Group assignment/randomization will be determined with a block-based matlab randomization.

Table 1: Study Measures I = intervention subject; P = partner subject

	Screening		Baseline	Interventions				Makeup Interventions (if needed)		Post-Intervention Assessments	
	Phone	In-Person		Week 1	Week 2	Week 3	Week 4	Week 5	Week 6	Immediate Post-Intervention	Final Post-Intervention
Study Activities											
Verbal Consent for Screening	I, P										
Inclusion/Exclusion (verified at In-Person)	I, P	I, P									
MRI Screening Form	I										
Informed Consent		I, P									
UBACC		I									
Demographics & background		I, P									
MoCA (V2)		I									
RAVLT		I (Lists C&D)								I (Lists A&B)	I (Lists C&D)
ADL-PI-self		I								I	I
PSS		I								I	I
PSQI		I								I	I
MFI		I								I	I
GDS-15		I		I	I	I	I	I	I		
AES		I, P								I, P	I, P
QoL-AD		I, P								I, P	I, P

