Exploratory aim. Examine the relationship between (a) NPS and (b) the coherence between structural and functional aspects of the NPS-shared neural circuit. We will conduct a connectome-based analysis to find structural connections that are unique to severity of NPI. The TN-PCA method⁵³ will be used to correlate with severity of NPI. We can replace the high dimensional tensor network summarizing an individual's brain connectome with a K-dimensional vector of brain PC scores; these scores can be used for visualizing variation among individuals in their brain connectomes and in statistical analyses studying relationships between structural and functional aspects of NPS-shared circuit and covariates. We will compare similarities of involved brain regions of NPS circuit for FC and WM across the entire sample at baseline. Quantitatively, we will use the Dice similarity coefficient to evaluate the percentage of overlapped regions. **To examine whether tDCS' effects on NPS-shared neural circuit and study partner-rated NPS depend on baseline WM integrity,** first we will compare the correlations between FC (at different time points) and baseline WM integrity on the overlapped regions between active vs. sham tDCS groups. We expect to see a higher correlation between FC and WM in active group in later time points. Next, using SVR described earlier⁵² we will examine the relationship between the sample's features (baseline WM tracts) and outcome (change of NPI severity or frequency scores).

Blood analysis plan: We will compare AD pathology markers from blood with changes of NPS, cognitive measures, and MRI data using correlational analyses. We will also examine if individuals with positive AD pathology respond differently to tDCS compared to those with negative AD pathology using ANOVA.

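### RAVLT Lists C&D are used at screening (the baseline) and again at the final visit, so the claim that alternate forms avoid practice effects does not hold for RAVLT at that visit (low severity)

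*Combined protocol and SAP*

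**What the plan says.** Section 4 (Study Design, Other measures) states that "Alternate forms of cognitive measures (EXAMINER, RAVLT, BVMTR) will be used across time points", "to avoid practice-effects", and refers the reader to Table 1.

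The same list of measures gives the number of forms for each instrument:

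- EXAMINER: "three different versions of the computer-based battery Executive Abilities".
- BVMT-R: "Test-Revised (BVMT-R, Forms 1-3".
- RAVLT: "two versions of the Rey Auditory Verbal Learning Test (RAVLT, Lists A&B and C&D".

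Table 1 in Section 8 assigns the forms to visits. Section 5 independently confirms the RAVLT version at screening, where the memory criterion is set against "population norms for the Rey Auditory Verbal Learning Test (RAVLT, Lists C&D". Table 1 shows no RAVLT in the baseline column. Section 8 explains that for eligible people "their screening data will be used as baseline data".

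Section 17 (Blood analysis plan) names one use of cognitive change: "We will compare AD pathology markers from blood with changes of NPS, cognitive measures, and MRI data using correlational analyses". It specifies neither the cognitive test nor the visit that supplies the change score.

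**The concern.** Two RAVLT versions cannot cover three administrations without a repeat, and the repeat falls on the two visits that define baseline-to-final change. That contrast compares a first with a second exposure to the same words. The baseline-to-post contrast compares two different lists. A reader of Section 4 would take both to be free of same-list practice.

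This matters mainly for the exploratory blood-marker analysis. Benefit from meeting a list again is itself a memory effect and could plausibly vary with AD pathology. If it does, a baseline marker could correlate with RAVLT change at the final visit, and so seem to predict response to the intervention, with no tDCS effect. Randomisation does not protect a correlation of this kind. Because Section 17 does not name the visit, nothing excludes the final-visit score.

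**Working it through.** **1. Forms by visit (Table 1, Section 8).**

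| Test | Baseline value | Immediate post-intervention | Final | Repeat? |
|---|---|---|---|---|
| RAVLT | C&D (in-person screening) | A&B | C&D | yes |
| EXAMINER | Form A (baseline) | Form B | Form C | no |
| BVMT-R | Form 1 (in-person screening) | Form 2 | Form 3 | no |

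Table 1 was flattened in conversion, but the RAVLT reading does not rest on the table alone. Section 4 counts two versions, and Section 5 places C&D at screening.

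**2. Time between the two C&D exposures.** The inputs are the visit windows in Sections 4, 4.2.2 and 8: screening to baseline, up to one month (about 4.3 weeks); baseline to intervention, up to 2 weeks; intervention, 4 weeks plus up to 2 for make-up sessions; intervention to post-assessment, up to 2 weeks; post-assessment to final, 4 to 6 weeks.

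- Minimum: 0 + 0 + 4 + 0 + 4 = 8 weeks.
- Maximum: 4.3 + 2 + 6 + 2 + 6 = 20.3 weeks.

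**3. Which contrasts are exposed.** Write mean observed change as practice gain p plus treatment effect d in the active arm, and p alone in the sham arm. The between-arm difference is (p + d) − p = d, whatever p is, provided p is the same in both arms. For example, with d = 1 point and p = 4 points the arms change by 5 and 4, and the difference is still 1. Within-arm change, and correlations of change with a baseline variable, do carry p.

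**4. Size in the marker correlation.** The plan gives no practice figure and no power figure for this analysis, so there is nothing to reproduce. The following are assumptions, in units of the RAVLT SD:

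- Retest correlation 0.7, so the variance of change without practice is 2(1 − 0.7) = 0.6.
- Practice gain varies between people with SD s and correlates ρ with the marker.
- The marker is otherwise unrelated to change.
- n = 40 × 0.9 = 36, from the enrolment target and 10% attrition in Section 17.

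The induced correlation is r = ρs / √(0.6 + s²). The two-sided 5% rejection rate uses Fisher's z, with mean shift atanh(r) × √(36 − 3).

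| s | ρ | r | Rejection rate |
|---|---|---|---|
| 0.2 | 0.2 | 0.05 | 6% |
| 0.3 | 0.3 | 0.11 | 10% |
| 0.3 | 0.5 | 0.18 | 18% |
| 0.4 | 0.7 | 0.32 | 48% |

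For the last row: r = 0.7 × 0.4 / √0.76 = 0.321, atanh(r) = 0.333, shift = 0.333 × 5.745 = 1.91, which against a critical value of 1.96 gives 48%. The nominal rate is 5%.

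**The case against.** Several points stand on the other side.

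- **The schedule alternates.** No list is used at consecutive visits, and Section 4 openly says there are two versions and points to Table 1. What the design fixes is repeat exposure, not a gain. In people with MCI, after 8 to 20 weeks and with another list in between, little list-specific learning may remain. This stands, and it is why the range starts near nominal.
- **The main comparisons are safe.** RAVLT sits among the other measures. The primary fMRI and secondary NPI endpoints do not use it. This stands.
- **The marker analysis is weak for other reasons.** A marker-change correlation that is not compared between arms cannot separate tDCS response from prognosis, regression to the mean or general test familiarity. Section 5 selects people on a low C&D score that then serves as baseline, so some rise is expected later on any list. With the same retest correlation of 0.7 and an assumed source-population mean between 0 and −1.5 SD, selection at −1 SD gives an expected rise of about 0.46 to 0.15 SD. This stands: the fix removes one source of distortion, not all of them.

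A reader might also infer that a false RAVLT improvement within an arm is likely. With 18 per arm, a retest correlation of 0.7 and an assumed gain of 0.2 to 0.5 SD, a one-sample t-test would reject in 18% to 73% of trials. The documents contain no such test. The within-group t-test in Section 17 is for LPG activation, and the model-based within-group change under H2a is for NPI measures.

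What the objection does not remove is the mismatch itself. Section 4 claims a property for RAVLT that its own schedule does not deliver at the final visit.

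**Conclusion.** The concern holds at low severity. Baseline-to-final RAVLT change is open to same-list practice, unlike EXAMINER and BVMT-R, and the sentence in Section 4 is inaccurate on this point. That part follows from the documents without any assumption.

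The consequence is confined to the exploratory blood-marker correlations, if they use RAVLT change at the final visit. Their false-positive rate from this source is about 6% to 48% at n = 36. The range rests entirely on assumed values: retest correlation 0.7, practice SD 0.2 to 0.4, and practice-marker correlation 0.2 to 0.7. The documents favour neither end.

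A reader might go further and conclude that follow-up RAVLT scores are necessarily inflated, or that the treatment comparison is biased. The documents support neither. They give no practice gain, and both arms follow the same form schedule, so the active-versus-sham contrast is unbiased if practice is equal in the two arms.

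**What to change.** Preferred: use a third RAVLT list at the final visit, as is already done with EXAMINER Form C and BVMT-R Form 3, and amend the RAVLT entry in Section 4 and the RAVLT row of Table 1. This depends on an equivalent third list being available, which the documents do not show.

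If none is available:

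- State in the blood analysis plan (Section 17) that marker correlations use screening-to-post RAVLT change (C&D to A&B).
- Limit final-visit RAVLT to the between-arm comparison.
- Reword the alternate-forms sentence in Section 4 so that it does not claim RAVLT practice effects are avoided at the final visit.

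The cost is one additional test form, or a few sentences of text. The downside of either route is that different lists may differ in difficulty. That difference is shared by both arms, so it does not bias the between-arm contrast, but it shifts mean change within an arm. Neither route turns a marker-change correlation without a control comparison into evidence of response to tDCS, because regression to the mean and prognosis remain.
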